10.2.4 Estimand Framework

Population

The population is similar to that for the primary endpoint. However, only participants with both baseline and at least one postbaseline stool consistency value from SBM during the Study Intervention Period will be included.

Variable

The variable is the change from baseline in the participant's 12-week stool consistency during the Study Intervention Period as derived from the twice daily eDiary (morning and evening).

Accounting for Intercurrent Events

Handling of intercurrent events will be similar to primary endpoint as discussed for the main analysis approach and first (MAR) sensitivity analysis.

In the second sensitivity analysis of imputing the missing data with worst response, missing postbaseline stool consistency value for SBM during Study Intervention Period will be imputed as Type 1 (looks like small hard lumps or balls, like pebbles).

Population Level Summary

Difference in means for secondary endpoint between linaclotide and placebo will be based on the following:

- Main Analysis Approach: Based on difference in LSMs from ANCOVA model
- Sensitivity Analysis 1 (MAR): Based on estimated difference from MMRM model in sensitivity analysis with MAR
- Sensitivity Analysis 2 (worst response imputation): Based on difference in LSMs from ANCOVA model

10.3 OTHER EFFICACY ENDPOINTS

The other efficacy endpoints are as follows:

- Overall SBM responders during the Study Intervention Period
- Weekly SBM + 2 responder during the Study Intervention Period
- Change from baseline in 12-week CSBM frequency rate (CSBMs/week) during the Study Intervention Period
- Change from baseline in 12-week abdominal pain (daytime, nighttime, and combined daytime and nighttime symptoms) during the Study Intervention Period
- Proportion of days with daytime fecal incontinence during the Study Intervention Period
- Change from baseline in 12-week straining during the Study Intervention Period
- Change from baseline in 12-week abdominal bloating (daytime, nighttime, and combined daytime and nighttime symptoms) during the Study Intervention Period
- Proportion of participants with an SBM within 24 hours after the first dose of study intervention
- Proportion of participants with an SBM within 48 hours after the first dose of study intervention

- Time to the first report of SBM after the first dose of study intervention
- Proportion of participants with an increase in rescue medicine or any other laxative, suppository, or enema use during 12-week Study Intervention Period
- Proportion of participants who report using rescue medicines or any other laxatives, suppositories, or enemas during 12-week Study Intervention Period
- Proportion of participants who no longer fulfill modified Rome III criteria for functional constipation at the end of the study intervention period
- Proportion of participants with each individual item score for the participant-completed global change items (pooping problems and tummy problems) at each week during Study Intervention Period
- Proportion of participants with each individual item score for the participant-completed global severity items (pooping problems and tummy problems) at each week during Study Intervention Period
- Change from baseline in participant-completed global severity items (pooping problems and tummy problems) at each week during Study Intervention Period
- Proportion of participants with each individual item score for the observer completed global change item and global severity item at each week during Study Intervention Period (collected for age group of 6-11 years only)

Overall SBM Responders During the Study Intervention Period

Overall SBM responders are defined as participants who have a change from baseline of ≥ 2 SBMs/week in the 12-week SBM frequency rate over the Intervention Period.

The above response threshold of at least 2-point change from baseline in 12-week SBM frequency rate (SBMs/week) to define the overall SBM responder may be revisited before unblinding based on the findings of blinded psychometric analysis to determine within participant clinically meaningful change. If this is the case, the revised response threshold will be documented in a SAP amendment.

To be qualified for an overall SBM responder, a participant must also meet the following conditions simultaneously:

- At least 4 weeks of study intervention duration,
- At least 48 completed diary days during the 12-week Study Intervention Period, and
- At least 4 completed diary days per analysis week in the last 4 intervention weeks

The participant needs to fill out both morning and evening diary on the same day to have a completed diary day.

The proportion of responders in the linaclotide group will be compared with the proportion in the placebo group using a CMH test controlling for age group (6 - 11 years of age versus 12 - 17 years of age). Participants who are not assessable for the responder parameters due to missing information are considered non-responders. The number and percentage of responders for each study intervention group, the difference in responder rates between the linaclotide group and the placebo group, the corresponding 95% confidence interval, Mantel-Haenszel based odds ratio and corresponding 95% confidence interval, and the 2-sided p-value associated with the CMH tests will be presented.

Weekly SBM + 2 Responder During the Study Intervention Period

For any week in the study intervention period, a weekly SBM + 2 responder is a participant who has an SBM increase ≥ 2 in the SBM weekly rate from baseline for that week. For the analysis week, if a participant did not have at least 4 full days (with both completed morning and evening diaries) of diary entries, the participant will not be considered a weekly SBM + 2 responder for that corresponding week.

The threshold of at least 2 to define the weekly SBM responder may be revisited before unblinding based on the findings of blinded psychometric analysis to determine within participant clinically meaningful change. If this is the case, the revised response threshold will be documented in a SAP amendment.

This responder endpoint will be analyzed in a similar way as discussed for the Overall SBM Responders endpoint.

Change From Baseline in Other Efficacy Endpoints Related to Bowel Habits and Abdominal Symptoms

The derivations of 12-week CSBM frequency rate (CSBMs/week), abdominal pain (daytime, nighttime, and combined daytime and nighttime symptoms), straining, and abdominal bloating (daytime, nighttime, and combined daytime and nighttime symptoms) during the Study Intervention Period are discussed in details from Sections 16.3.4 to 16.3.8.

For change from baseline in 12-week CSBM frequency rate (CSBMs/week), 12-week abdominal pain (daytime, nighttime, and combined daytime and nighttime symptoms), 12-week straining, and 12-week abdominal bloating (daytime, nighttime, and combined daytime and nighttime symptoms), the linaclotide group will be compared to the placebo group using the same ANCOVA model as discussed for primary endpoint in main analysis approach (Section 10.1.1).

Cumulative distribution function plots will also be provided for the change from baseline other efficacy endpoints by study intervention group.

By-week summary of the other efficacy endpoints will be provided by study intervention group.

Proportion of Days with Daytime Fecal Incontinence During the Study Intervention Period

Fecal incontinence will be collected daily in the evening eDiary. Participants are asked a question (as discussed in Section 16.3.9) regarding episodes of fecal incontinence in the evening diary. A "yes" response to that question will be counted as presence of daytime fecal incontinence in the corresponding day. The proportion of days with daytime fecal incontinence during the Study Intervention Period will be derived based on number of non-missing reported days with fecal incontinence responses during the Study Intervention Period in the denominator.

Descriptive statistics (mean, median, SD, standard error of mean, minimum, and maximum) by study intervention group will be provided.

Proportion of Participants with an SBM within 24 Hours of First Dose of Study Intervention

A participant is a 24-hour responder if the participant has at least 1 SBM within 24 hours of first dosing of study intervention. Any SBM reported in the evening diary on randomization day and in the morning diary at the day after first dose date (i.e., Day 2) will be considered a SBM within 24 hours. The proportion of responders will be analyzed in a similar way as discussed earlier for SBM responder endpoints.

Proportion of Participants with an SBM within 48 hours of First Dose of Study Intervention

A participant is a 48-hour responder if the participant has at least 1 SBM within 48 hours of first dosing of study intervention. Any SBM reported from the evening diary on randomization day to the morning diary on the second day after first dose date (i.e., Day 3) will be considered a SBM within 48 hours. The proportion of responders will be analyzed in a similar way as discussed earlier for SBM responder endpoints.

Time to First Report of SBM After the First Dose of Study Intervention

Time to first report of SBM after the first dose of study intervention (i.e. time to diary reporting with first SBM) is defined as the number of hours elapsed from the first dose of study intervention taken to the diary reporting time with the first SBM. Reporting may not occur in real time; first eDiary reporting will be approximately within 12 hours after the first dose with all subsequent reports occurring in 12-hour spans twice daily (morning and evening) Participants who do not achieve an SBM during the Intervention Period will be considered censored, with the censoring time defined as number of hours elapsing from the first dose of study intervention taken to 11:59 AM (morning diary end period) on the day after last dose date.

Proportion of Participants With an Increase in Rescue Medicine or Any Other Laxatives, Suppositories, or Enema Use During 12-week Study Intervention Period

The proportion of participants who have an increase from baseline in the percentage of days using rescue medicine or any other laxatives, suppositories, or enemas in the linaclotide dose group during the 12-week Intervention Period will be compared to the proportion in the placebo group using a CMH test controlling for age group. The number and percentage of responders for each study intervention group, the difference in responder rates between the linaclotide group and the placebo group, the corresponding 95% confidence interval, Mantel-Haenszel -based odds ratio and corresponding 95% confidence interval, and the 2-sided p-value associated with the CMH tests will be presented.

Proportion of Participants Who Report Using Rescue Medicines or Any Other Laxative, Suppositories, or Enema During 12-week Study Intervention Period

The proportion of participants who report using rescue medicines or any other laxative, suppositories, or enemas during the Study Intervention Period in the linaclotide group will be compared with the proportion in the placebo group using a CMH test controlling for age group. The similar analyses as discussed for the proportion of participants with an increase in rescue medicine or any other laxatives, suppositories, or enema use will be provided by study intervention group.

Participant-Completed Global Change Items and Global Severity Items at Each Week During Study Intervention Period

The details of participant-completed global change item scores and global severity item scores are discussed in Section 16.3.10. For each of the participant-completed global change items (pooping problems and tummy problems) and global severity items (pooping problems and tummy problems), study intervention comparison (linaclotide versus placebo) will be performed using a CMH test, controlling for age group at each week after randomization during the Study Intervention Period. Counts and percentages for each category within each individual item will be provided by study intervention group.

Change from baseline in the participant-completed global severity items (pooping problems and tummy problems) at each post baseline week during the Study Intervention Period will also be analyzed using the same ANCOVA model as discussed for primary endpoint in main analysis approach (Section 10.1.1).

Observer-Completed Global Change Item and Global Severity Item at Each Week During Study Intervention Period

The observer-completed global change item and global severity item will be assessed on a weekly basis in the eDiary, for the 6 - 11 years of age group only as discussed in Section 16.3.11. Summary statistics of observer-completed global items will be provided by study intervention group in the 6 - 11 years of age group at each week during the Study Intervention Period. Counts and percentages for each category of global change item and global severity item will be provided by study intervention group.

Proportion of Participants Who No Longer Fulfill Modified Rome III Criteria for FC at the End of the Study Intervention Period

The details of the derivation of this endpoint are discussed in Section 16.3.12. The proportion of participants who no longer fulfill modified Rome III criteria for FC at the end of the study intervention period will be presented by study intervention group.

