#### 5.1. Inclusion Criteria

The targeted participant population will include male and female participants, 6 to 17 years of age (FC participants) and 7 to 17 years of age (IBS-C participants). Randomization of FC participants will be stratified by age group only (6 to 11 years of age versus 12 to 17 years of age) with a minimum of 40% of participants within each age group. Randomization of IBS-C participants will be stratified by age group only (7 to 11 years of age versus 12 to 17 years of age) with a minimum of 40% of participants within each age group.

Participants are eligible to be included in the study only if all of the following criteria apply (unless stated otherwise, criteria apply to both FC and IBS-C participants):

1.	Age and Weight
1.01	Male and female participants must be ages 6 to 17 years (FC participants) or ages 7 to 17 years (IBS-C participants) (inclusive) at the time the participant provides assent for the study and parent/guardian/legally authorized representative (LAR) has provided signed consent
1.02	Participant weighs $\geq 18$ kg at the time the participant provides assent and the parent/guardian/LAR has provided signed consent

2.	Type of Participant and Disease Characteristics
2.01	
Participants who meet the modified Rome III criteria for Child/Adolescent FC. For at least 2 months before the Screening Visit, the participant has had 2 or fewer defecations (with each defecation occurring in the absence of any laxative, suppository, or enema use during the preceding 24 hours) in the toilet per week. In addition, participant meets one or more of the following criteria at least once per week for at least 2 months before the screening visit:
 
 
• History of retentive posturing or excessive volitional stool retention
 
• History of painful or hard BMs
 
• History of large diameter stools that may obstruct the toilet
 
• Presence of a large fecal mass in the rectum
 
• At least 1 episode of fecal incontinence per week
 

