### **Fecal Incontinence - Daytime**

Participants will record their episodes of fecal incontinence by responding to the following assessment in their evening eDiary.

- From when you got up this morning until now, did you have a pooping accident (even a little)?
  - Yes
  - No

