
 
• Any clinically significant abnormal laboratory findings or other abnormal safety assessments that are associated with the underlying disease, unless judged by the investigator to be more severe than expected for the participant’s condition. Merely repeating an abnormal test, in the absence of any of the above conditions, does not constitute an AE. Any abnormal test result that is determined to be an error does not require recording as an AE.
 
• The disease/disorder being studied or expected progression, signs, or symptoms (clearly defined) of the disease/disorder being studied, unless more severe than expected for the participant’s condition.
 
• The following disease-related events (DREs) are common in participants with FC and can be serious/life threatening:               
 
○ Abdominal bloating
 
○ Straining
 
○ Sense of incomplete evacuation
 
○ Fecal incontinence
 
 
If the investigator considers these manifestations to have a reasonable possibility of relationship to the study intervention(s), then they should be reported as AEs or SAEs.
 
 
• Medical or surgical procedure (eg, endoscopy, appendectomy): the condition that leads to the procedure is the AE
 
• Situations in which an untoward medical occurrence did not occur (social and/or convenience admission to a hospital)
 
• Anticipated day-to-day fluctuations of pre-existing disease(s) or condition(s) present or detected at the start of the study that do not worsen
 

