Nominal p-values will be provided for the other efficacy endpoints as discussed in Section 10.3.

Depending on the enrollment status for FC participants in this study, an interim analysis (IA) for futility may be considered (details in Section 13.0). A futility check in this IA (when performed) will be performed based on the pre-selected non-binding futility boundary. Following a conservative approach, the final analysis will be performed at a slightly reduced alpha level of 0.049 (2-sided) in case this futility IA is conducted. The optional futility IA at 50% information is not planned to stop the study for efficacy.

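### Daytime fecal incontinence in FC is only described by arm on treatment, which gives up precision and leaves relief of existing incontinence mixed with new onset

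*SAP*

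**What the plan says.** The protocol (Section 9.1.5.1.1) lists the proportion of days with daytime fecal incontinence among the other efficacy endpoints for FC. It comes from a yes/no item in each evening diary (Section 8.1.1.3). FC SAP Section 10.3 says the proportion "will be derived based on number of non-missing reported days with fecal incontinence responses during the Study Intervention Period in the denominator", and the planned output is "Descriptive statistics (mean, median, SD, standard error of mean, minimum, and maximum) by study intervention group will be provided".

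For the neighboring daily endpoints (CSBM rate, abdominal pain, straining, bloating), the same section says "the linaclotide group will be compared to the placebo group using the same ANCOVA model as discussed for primary endpoint". Days of rescue or laxative use are also judged against baseline there, with a difference, intervals and a CMH p-value.

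FC SAP Section 10.0 states: "Nominal p-values will be provided for the other efficacy endpoints as discussed in Section 10.3". The protocol makes the same promise below Table 9-2, without the cross-reference. The incontinence paragraph in Section 10.3 names no test. A further sentence, "By-week summary of the other efficacy endpoints will be provided by study intervention group", sits in the change-from-baseline subsection, so it is unclear whether it covers incontinence.

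**The concern.** Baseline incontinence will differ widely between children. In inclusion criterion 2.01, "At least 1 episode of fecal incontinence per week" is one of five alternative qualifying features, so some children will have it often and others never. Adjusting for a baseline like this normally sharpens a comparison, and the plan does so for the other daily symptoms.

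The endpoint can also move both ways. The protocol describes incontinence in FC as usually overflow from impaction (Section 2.1), which treatment might relieve. It also names incontinence among the possible consequences of diarrhea (Section 2.2.1), the most frequent adverse event with linaclotide. One on-treatment mean per arm blends the two.

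Adverse event reporting is only a partial cross-check. Protocol Section 10.3.1 lists fecal incontinence as a disease-related event and says: "If the investigator considers these manifestations to have a reasonable possibility of relationship to the study intervention(s), then they should be reported as AEs". The diary is therefore the only systematic measure of incontinence that does not depend on the investigator's judgment.

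**Working it through.** **The plan's own figure.** No sample size or power is stated for incontinence. The FC calculation for the primary endpoint (FC SAP Section 14.0: difference 1, SD 3, two-sided 5%, 85% power, 163 per arm) reproduces: 162 per arm by the normal formula, and with 163 per arm a power of 85.3% (normal) or 85.1% (t). So 163 per arm is used below.

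**What the planned output already supports.** For two arms of 163, the standard error of the unadjusted difference is SD × √(2/163) = 0.1108 SD. The 95% half-width is 1.96 × 0.1108 = 0.217 SD. The difference detectable with 85% power is (1.960 + 1.036) × 0.1108 = 0.332 SD. The documents give no SD for this endpoint. For an assumed SD of 0.10 to 0.30 in the proportion of days, the half-width is 2.2 to 6.5 percentage points and the detectable difference 3.3 to 10.0 points.

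**What baseline adjustment would add.** ANCOVA multiplies the standard error by √(1 − r²), where r is the correlation between baseline and on-treatment percentages. The documents give no r, so a range is assumed:

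| r | √(1 − r²) | Half-width (SD) | Narrower by |
|---|---|---|---|
| 0.3 | 0.954 | 0.207 | 5% |
| 0.5 | 0.866 | 0.188 | 13% |
| 0.7 | 0.714 | 0.155 | 29% |
| 0.8 | 0.600 | 0.217 × 0.600 = 0.130 | 40% |

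An unadjusted change score is not a substitute. With equal variances its factor is √(2(1 − r)), which is 1.18 at r = 0.3 and 1.00 at r = 0.5, so it is no better than the plan unless r exceeds 0.5.

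**Whether the baseline exists.** The diary is completed morning and evening throughout the Preintervention Period (protocol Section 10.10.2). FC SAP Section 10.0 takes baselines for daily diary endpoints from the 14 days before randomization. Criterion 2.04 requires at least 10 of those 14 days to be complete. The data are therefore available, but Section 10.0 does not name incontinence among the baselines to be derived.

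**Whether opposing effects can be separated.** Let p be the share of children with incontinence at baseline, d₁ the mean effect in them and d₀ the mean effect in the rest. The difference between arm means estimates p·d₁ + (1 − p)·d₀. It is zero whenever p·d₁ = −(1 − p)·d₀, for example when relief in the first group offsets new accidents in the second. Randomization does not change this, and p, d₁ and d₀ cannot be recovered from the planned statistics. An ANCOVA difference is also a net mean and cancels in the same way. Only a split by baseline status addresses it.

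**The case against.** The strongest reply is that little is lost. The summary is by study intervention group, so placebo stands beside linaclotide with its mean, SD and standard error. Allocation is randomized 1:1 within age group, so the on-treatment contrast is valid without a baseline, and chance imbalance is already reflected in the standard errors. All of this stands. A reader might infer that there is no comparison with placebo, or that the trial cannot say whether 72 µg helps or worsens incontinence. The documents support neither reading.

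A reader might also infer that adverse event reporting is set up to leave this harm out. That goes too far. Besides events judged possibly drug-related, Section 10.3.1 makes disease symptoms reportable when they are more severe than expected, and treats an increase in frequency or intensity of a pre-existing condition as an adverse event. Diarrhea gets particular attention, and stool consistency is the formally tested secondary endpoint.

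Further points reduce the weight. The endpoint lies outside the multiplicity procedure. The protocol itself defines it as an on-treatment proportion and leaves the analysis to the SAP. Modified Rome III resolution and the observer global items are also only described. The planned baseline summary of bowel habits and symptoms (FC SAP Section 8.0) could be read to include incontinence, though it does not name it. The percentages are likely to be skewed, which makes a normal-theory model approximate.

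None of this supplies a prespecified difference, interval or p-value, reconciles the paragraph with the nominal p-value statement, or separates relief from new onset.

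**Conclusion.** The point holds as a gap in specification, precision and interpretation. It does not make the comparison invalid. The plan gives daytime fecal incontinence less than the other daily symptoms without a reason, and its incontinence paragraph does not deliver the nominal p-value that protocol and SAP both announce. With 163 per arm the crude interval has a half-width of about 0.22 SD. Baseline adjustment would narrow it by 5% to 40%, and that range rests wholly on the assumed r of 0.3 to 0.8. The inability to separate relief from new onset does not depend on r. No stated sample size or power figure changes. This should be corrected, but it does not threaten the primary conclusion.

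**What to change.** In FC SAP Sections 10.0 and 10.3:

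- Define the baseline percentage of days with daytime fecal incontinence over the 14 days before randomization, with non-missing evening entries as the denominator.
- Analyze the change from baseline with the Section 10.1.1 ANCOVA (arm, age group, baseline), reporting the LSM difference, 95% CI and nominal p-value. This also settles the mismatch with Section 10.0.
- Beside the model, tabulate by arm (a) the change among participants with at least 1 incontinence day at baseline and (b) the number and percentage with none at baseline and at least 1 day on treatment. Read (b) against placebo: 12 weeks of treatment offer far more evenings for a first event than 14 baseline days, so some apparent new onset is expected in both arms.

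The cost is SAP wording and one added table, with no new data, participants or alpha. The downside is that the model is approximate for skewed percentages, which is a further reason to show (a) and (b) next to it.

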Serum Pregnancy Tests ⁿ	X							
Urine Pregnancy Tests ^o			X		X	X	X	
Urine Drug Screen ^p	X							
AE Evaluation	X	X	X	X	X	X	X	X
Prior and Concomitant Medications	X	X	X	X	X	X	X	X
Rescue Medication Dispensed ^q		X	X	X	X	X	X	
eDiary and Instructions Given to Participant/Caregiver ^r		X						
eDiary Compliance ^r			X	X	X	X	X	X
eDiary Eligibility Report ^f			X					
Study Intervention Administered on Site ^s			X					
Study Intervention Dispensed			X		X	X		
Study Intervention and Rescue Medication Compliance and Accountability			X ^s	X	X	X	X	X ^t

AE = adverse event; ECG = electrocardiogram; eDiary = electronic diary: refers to the participant- or interviewer-administered version of the PRO diary on a handheld electronic device; IWRS = interactive Web response system; PRO = patient reported outcome.

- a. Study procedures for screening in LIN-MD-66 can be combined with End of Treatment (EOT)/Week 12 Visit (Visit 7) for Study LIN-MD-64.
- b. Participants who rollover to the long-term safety study, LIN-MD-66, before the EOS Visit (Visit 8) are not required to have this visit.
- c. Participants must complete at least 12 weeks (84 days) of study intervention before arriving at the study site for the EOT/Week 12 Visit (Visit 7). All randomized participants who prematurely discontinue from the study intervention, regardless of cause, should complete assessments at this EOT/Week 12 Visit (Visit 7).
- d. The parent/guardian/legally authorized representative must provide written informed consent and the participant must provide assent before the participant's enrollment in the study. If a parent or legal guardian is also the participant's caregiver, he or she will be asked to sign a combined parent and caregiver written informed consent. Caregivers other than parent or legal guardian must provide written informed consent.
- e. Prior to dosing, the investigator or appropriate site staff member will assess if Rome IV criteria for Child/Adolescent FC (FC and IBS-C participants) or Rome IV criteria for Child/Adolescent IBS (IBS-C participants) was met and record the outcome in the eCRF. Eligibility for the study is not based on this assessment.
- f. Eligibility report must be run prior to randomization.

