6.3 MODIFIED INTENT-TO-TREAT POPULATION

The Modified Intent-to-Treat (mITT) Population will consist of all participants in the Randomized Population who receive at least 1 dose of double-blind study intervention. Participants will be summarized according to the randomized study intervention for all efficacy analysis variables/endpoints.

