16.3 DERIVED VARIABLES

16.3.1 Missed Morning/Evening eDiary Assessments

No imputation or derivation will be performed for missed morning/evening assessments unless otherwise specified.

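### FC time to first SBM report is measured by diary but censored by last dose, so a child who stops the diary and keeps dosing is counted as SBM-free for time nobody observed

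*SAP*

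**What the plan says.** FC SAP Section 10.3 defines the event time as "the number of hours elapsed from the first dose of study intervention taken to the diary reporting time with the first SBM". Reports come about every 12 hours: "first eDiary reporting will be approximately within 12 hours after the first dose". An SBM therefore exists for this endpoint only if a completed diary records it.

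For everyone else: "Participants who do not achieve an SBM during the Intervention Period will be considered censored". The censoring time runs from "the first dose of study intervention taken to 11:59 AM (morning diary end period) on the day after last dose date". That date comes from the dosing record, and the last diary plays no part in it. If the last dose date is missing, FC SAP Section 16.5 substitutes the day before Visit 7, which is also not a diary date.

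The analysis set is set out in FC SAP Section 6.3: "The Modified Intent-to-Treat (mITT) Population will consist of all participants in the Randomized Population who receive at least 1 dose of double-blind study intervention". For diaries that were missed altogether, Section 16.3.1 says: "No imputation or derivation will be performed for missed morning/evening assessments unless otherwise specified".

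**The concern.** The event is seen through one instrument and follow-up is measured by another. When the diary ends before dosing does and no SBM has been reported, the rule adds the time between the two to the risk set as if the diary had been kept and no SBM had occurred.

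This sits badly with the rest of the FC SAP. Section 10.0 takes an observed-cases approach to missing postbaseline data. Section 16.3.4 bases SBM rates on the days actually contributed. The fecal incontinence endpoint in Section 10.3 uses only days with a response.

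No other provision clearly repairs it. The rule that a child who cannot be assessed is a non-responder covers responder endpoints only, and the missing-data sensitivity analyses cover only the primary and secondary endpoints.

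At stake are the late part of the time-to-event curve and any comparison of arms that uses the ordering of times. Once most children have had a first SBM, a few who are wrongly still at risk weigh heavily.

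**Working it through.** The documents give no event count, power or drop-off rate for this endpoint, so there is no stated figure to reproduce.

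**1. Censoring time under the written rule.** Inputs: completers dose for at least 84 days (FC SAP Table 4-1: "Participants must complete at least 12 weeks (84 days) of study intervention before arriving at the study site"); first dose on Day 1, assumed between 08:00 and 16:00. Formula: 11:59 on (last dose day + 1) minus first dose time.
- Last dose Day 84, first dose 10:00: 84 × 24 h + 1 h 59 min ≈ 2,018 h. Over 08:00 to 16:00 the range is 2,020 down to 2,012 h, or 84.2 to 83.8 days.
- Last dose Day 1, first dose 10:00: 26 h. Last dose Day 28: 28.1 days.

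**2. Time actually observed.** If the only post-dose diary is the Day 1 evening one (assumed 21:00), observation ends 5 to 13 h after first dose. With no post-dose diary it is 0 h.

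**3. Effect on the curve.** Assume 163 in one arm, exponential time to first report with a median of 48 h, a 12-h grid, and *k* children who file only the Day 1 evening diary but dose to Day 84.
- Written rule: S(t) = [(163 − k)·2^(−t/48) + k] / 163. For k = 8 at 168 h: (155 × 0.0884 + 8)/163 = 0.133.
- Last-diary censoring: S(t) = [1 − (163 − k)(1 − q)/163]·q^(t/12 − 1), with q = 2^(−12/48) = 0.841. For k = 8 at 168 h: 0.849 × 0.105 = 0.089.

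| k | Day 7, rule | Day 7, last diary | Day 14, rule | Day 14, last diary |
|---|---|---|---|---|
| 2 | 0.100 | 0.089 | 0.020 | 0.008 |
| 8 | 0.133 | 0.089 | 0.057 | 0.008 |
| 16 | 0.178 | 0.090 | 0.105 | 0.008 |

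Under the rule the curve levels off at k/163 (1.2%, 4.9%, 9.8%) instead of near zero. The estimated median on the grid is 60 h under both rules for every k shown. With an assumed median of 96 h and k = 16 it moves by one 12-h step (120 against 108 h).

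**4. Effect on a rank-based test.** The test is assumed, since the SAP names none: log-rank, 163 per arm, exponential times, placebo median 48 to 72 h, hazard ratio 1.4, diary stopped within 24 to 72 h, dosing to Day 84, 2,000 to 3,000 simulated trials per scenario.
- No drop-off: power about 85 to 87%.
- 1% per arm (1 to 2 children): 76 to 81%. 2% per arm (about 3 children): 69 to 76%. Last-diary censoring keeps 83 to 87%. The balanced loss is 4 to 14 points.
- If 10% per arm truly have no SBM in 12 weeks (assumed), the balanced loss falls to about 1 to 4 points.
- Unequal drop-off, linaclotide against placebo: 46 to 62% at 3% against 1%. Reversed, at 1% against 3%, the rule slightly raises power (88 against 85%).
- No drug effect: the nominal 5% rejection rate becomes 6.5 to 10% at 3% against 1%, including the 10% no-SBM variant.

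**The case against.** The strongest reply is that the affected group is small. To be randomized, a child must have completed both diaries on 10 of the 14 preceding days (protocol criterion 2.04). That child must then stop before reporting any SBM, keep taking capsules, and continue despite diary checks at Weeks 2, 4, 8 and 12. This stands as a limit on size. It does not correct the rule: the first post-dose check is at Day 15, and it cannot recover missed reports.

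A second reply is that the observed-cases principle can be read as leaving out a child with no post-dose diary. For that child the text is indeed ambiguous. A child with an early diary is plainly within the censoring sentence.

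Third, early onset is also covered by the 24-hour and 48-hour responder endpoints, where a child who cannot be assessed counts as a non-responder. That reduces reliance on this endpoint.

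A reader might infer that the SAP amendment created the problem. It did not. Protocol Section 9.1.4 already admitted any dosed child with one postbaseline entry on the SBM items, which includes a child with only a Day 1 evening diary. The amendment adds children with no postbaseline diary at all.

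A reader might also infer that every early diary stopper is credited with about 84 days. Only a child who doses to about Day 84 is; one who also stops dosing on Day 1 is censored at about 26 hours.

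**Conclusion.** The rule as written counts unobserved time as SBM-free whenever the diary stops before dosing does and no SBM has been reported. That follows from the text alone. For children who keep the diary it is harmless, because their last Intervention Period diary is the morning one after the last dose.

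The size cannot be fixed from the documents. The effect lies in the tail of the curve and in a rank-based comparison, and the median barely moves. Under assumed balanced drop-off of 1 to 2% per arm the loss is roughly 1 to 14 points of power. With unequal drop-off it can be larger and can go in either direction. The large losses under imbalance illustrate sensitivity; no passage supports those rates.

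Nor do the documents support reading this as a threat to the trial's type I error. The endpoint is one of 17 listed as 'other', outside the sequential procedure, and FC SAP Section 10.0 says only: "Nominal p-values will be provided for the other efficacy endpoints as discussed in Section 10.3". The primary and secondary tests are untouched. The priority is minor.

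**What to change.** Replace the censoring sentence in FC SAP Section 10.3 with wording to this effect:

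> Participants with no reported SBM are censored at the reporting time of their last completed morning or evening diary in the Intervention Period, and no later than 11:59 AM on the day after the last dose. Participants with no post-dose diary are censored at time 0.

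This is one sentence pair in the SAP and one line of derivation code, with no new data. Less nominal follow-up will be reported. Last-diary censoring still assumes that stopping the diary is unrelated to bowel outcome, and it does not deal with gaps before the first report; a short note should say so.

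As a secondary clarification in the same edit, the SAP can name the analysis, for example Kaplan-Meier estimates with a log-rank test stratified by age group. At present the paragraph ends at the censoring rule.
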